2.5 Analysis of the primary objective

2.5.1 Primary endpoint

The primary outcome measure of the study will be the proportion of patients remaining on treatment with LCZ696 97 mg sacubitril / 103 mg valsartan at six months of follow up. The proportion will be calculated as the number of patients at 97 mg sacubitril / 103 mg valsartan over the total number of patients that received at least one dose of LCZ696.

2.5.2 Statistical hypothesis, model, and method of analysis

The data analysis will be primarily descriptive. Therefore, there is no a-priori hypothesis being tested.

The primary efficacy outcome will be assessed by the proportion of patients on LCZ696 97 mg sacubitril / 103 mg valsartan bid at 6 months of treatment. 95% confidence interval using binomial proportion will be calculated for the estimate of the proportion in order to assess precision and make inferences to the target population.

Novartis	For business use only	Page 13
SAP		PARASAIL / LCZ696BCA02

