## 5.5 **Treating the patient**

#### 5.5.1 **Patient numbering**

Each patient is uniquely identified by a Subject Number which is composed by the site number assigned by Novartis and a sequential number assigned by the investigator. Once assigned to a patient, the Subject Number will not be reused.

Confidential

Upon signing the informed consent form, the patient is assigned the next sequential number as given by the investigator using the next blank CRF book available from the EDC system.

If a screened patient fails to be enrolled in the study or treated for any reason, the reason will be entered on the Screening Study Disposition CRF.

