## 5.5.5 Instructions for prescribing and taking study treatment

During the baseline visit all patients will be instructed to stop taking their ACEIs for 36 hours prior to taking the first dose of LCZ696. Patient receiving an ARBs will only have to discontinue their medication and start LCZ696 at the next schedule time. All patients will be initiated on LCZ696 at 24 mg sacubitril / 26 mg valsartan that can be up-titrated to LCZ696 49 mg sacubitril / 51 mg valsartan bid after 2-4 weeks and then up-titrated again to 97 mg sacubitril / 103 mg valsartan bid after another 2 – 4 weeks. Timing of LCZ696 up-titration will be dependent on patient tolerability and the judgement of the physician.

If patients experience any lack of tolerability including but not limited to hypotension and hyperkalemia, the dose of LCZ696 may be reduced or treatment suspended or terminated as per the judgement of the treating physician.

All dosages prescribed and dispensed to the patient and all dose changes during the study must be recorded on the Dosage Administration Record CRF.

The investigator should promote compliance by instructing the patient to take the study treatment exactly as prescribed and by stating that compliance is necessary for the patient's safety and the validity of the study. The patient should be instructed to contact the investigator if he/she is unable for any reason to take the LCZ696 as prescribed.

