# 9.6 Sample size calculation

The primary outcome measure for the current study will be the proportion of patients on 97 mg sacubitril / 103 mg valsartan bid of LCZ696 at 6 months of treatment. The data from clinical trials have shown that at 12 weeks (3 months) approximately 80% of patients have achieved this dose. In this current real – life study of 6 months (primary endpoint) a reasonable estimate of patients achieving this dose would be 70%.

Confidential

Given that this is a single cohort, prospective study in which all patients are receiving the same treatment and the objective is to describe the proportion of patients reaching 97 mg sacubitril / 103 mg valsartan bid LCZ696, sample size requirements are based on the precision of the estimate. This is assessed with the 95% confidence interval. A reasonable level of precision is one with a 95% confidence interval width ( $\omega$ ) that is between 5 and 15% of the point estimate. With 300 patients enrolled in the study, the 95% Confidence Interval width will be ± 5.2% which is equivalent to 7.4% of the point estimate of 70%, with upper and lower limits of 64.8% – 75.2% respectively. This is within the limits of reasonable precision.

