5.4 Statistical models

5.4.1 Primary anlysis

For the proportion and percentage along with 95% confidence limits estimated using normal approximation (binomial proportion), statistical programmer may use the following code:

```
<Sample code>
proc freq data= <xxx>;
tables <xxx> / binomial;
run;
```

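### The primary 95% interval and the planned ±5.2 points assume independent patients; if month 6 dose status is correlated within sites, both overstate precision, by an amount the documents do not allow one to fix.

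*SAP*

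**What the plan says.** The primary endpoint is the number of patients on 97/103 mg bid at month 6, divided by all patients who took at least one dose (Protocol 6.4.1, SAP 2.5.1). SAP 2.5.2 gives the analysis: "95% confidence interval using binomial proportion will be calculated for the estimate of the proportion in order to assess precision". The same sentence, like Protocol 9.4.3, adds that the interval is for inference to the target population. SAP 5.4.1 specifies limits "estimated using normal approximation (binomial proportion" and supplies PROC FREQ code with the binomial option and no site or cluster term. SAP 2.7.2 uses the same kind of interval for the month 12 proportion.

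The sample size is justified by precision only. Protocol 9.6, repeated in SAP 3, takes 70% as the expected proportion and states: "With 300 patients enrolled in the study, the 95% Confidence Interval width will be ± 5.2" (percent). It calls this 7.4% of the point estimate and compares it with a criterion of 5 to 15%.

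The study is multi-centre (Protocol 3.1). Under Protocol 5.5.5 the timing of up-titration "will be dependent on patient tolerability and the judgement of the physician", and reduction, suspension or termination is left to the treating physician. Neither document gives a planned number of sites, a cap per site, an ICC, a design effect or an analysis that accounts for site.

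**The concern.** The endpoint is a dose level, and a physician helps to decide it: when to move up, whether to reduce other drugs first (Protocol 5.5.6), and whether to step down. Some of the information behind those decisions is also gathered locally. Blood pressure is measured by routine practice (Protocol 6.6.2) and laboratory tests are done as routine care (Protocol 6.6.5), while potassium, blood pressure and eGFR can all prompt a dose change (Protocol 5.5.10). Patients of one site share these habits, so their month 6 dose status may be positively correlated. The binomial variance p(1 − p)/n sets that correlation to zero.

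No hypothesis is tested, so the interval is the plan's statement of uncertainty about its main result. If sites were treated as fixed and inference stopped at them, the binomial interval would not be too narrow. Because the interval is meant to reach beyond the participating sites, variation between sites belongs in it.

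**Working it through.** **Inputs from the documents.** n = 300 and p = 0.70 (Protocol 9.6); two-sided 95%, z = 1.96, normal-approximation interval (SAP 2.5.2 and 5.4.1).

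**Assumed inputs, because the documents give none.** 15, 30 or 60 sites of equal size, so m = 20, 10 or 5 patients per site; ICC 0.01, 0.05 or 0.10. To judge these ICCs, the standard deviation of the true site proportions is √(ICC × 0.7 × 0.3): 4.6, 10.2 and 14.5 points respectively.

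**Step 1: reproduce the plan's figure.** 1.96 × √(0.7 × 0.3 / 300) = 0.0519, or 5.19 points. The limits are 64.8% to 75.2%, and 5.19 / 70 = 7.4%. The stated figure reproduces exactly, so it contains no allowance for clustering.

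**Step 2: allow for clustering.** Design effect DE = 1 + (m − 1) × ICC. Half-width = 5.19 × √DE. Actual coverage of the unadjusted interval = 2Φ(1.96 / √DE) − 1.

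For example, with 30 sites and ICC 0.05: DE = 1 + 9 × 0.05 = 1.45; half-width = 5.19 × 1.204 = 6.24 points; coverage = 2Φ(1.628) − 1 = 89.6%; effective sample size = 300 / 1.45 = 207.

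| Sites × patients | ICC | DE | Half-width (points) | Half-width as % of 70% | Coverage of unadjusted interval |
|---|---|---|---|---|---|
| 60 × 5 | 0.01 | 1.04 | 5.29 | 7.6% | 94.5% |
| 60 × 5 | 0.05 | 1.20 | 5.68 | 8.1% | 92.6% |
| 60 × 5 | 0.10 | 1.40 | 6.14 | 8.8% | 90.2% |
| 30 × 10 | 0.01 | 1.09 | 5.41 | 7.7% | 94.0% |
| 30 × 10 | 0.05 | 1.45 | 6.24 | 8.9% | 89.6% |
| 30 × 10 | 0.10 | 1.90 | 7.15 | 10.2% | 84.5% |
| 15 × 20 | 0.01 | 1.19 | 5.66 | 8.1% | 92.8% |
| 15 × 20 | 0.05 | 1.95 | 7.24 | 10.3% | 84.0% |
| 15 × 20 | 0.10 | 2.90 | 8.83 | 12.6% | 75.0% |

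A beta-binomial simulation (100,000 runs per scenario) of 30 sites at ICC 0.01, 0.05 and 0.10 gave coverage of 93.8%, 89.5% and 84.2%, in line with the formula.

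**Step 3: compare with the plan's own criterion.** The plan applies its 5 to 15% limit to the half-width (7.4%), so the ceiling is 0.15 × 70 = 10.5 points. Reaching it needs DE = (10.5 / 5.19)² = 4.1. That is an ICC of about 3.1 / 9 = 0.34 at 10 patients per site, or 3.1 / 19 = 0.16 at 20 per site. Every row of the table is below the ceiling.

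**The case against.** The strongest objection is that the harm rests on inputs that are not in the documents. With many small sites and little variation the effect is trivial: 60 sites at ICC 0.01 give ±5.3 points against ±5.2. The 75% coverage figure needs the fewest sites and the highest ICC together. This stands, and it is why the point is conditional.

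Second, the protocol limits discretion. There is one starting dose and a titration scheme tied to the product monograph. Two steps of 2 to 4 weeks each should be complete 4 to 8 weeks after the start, well before month 6. Investigators are to try to hold the target dose and to consider other drugs before stepping down. The sentence on physician judgement in Protocol 5.5.5 concerns timing, and it names patient tolerability first. This weakens the mechanism without removing it, because whether to step down or stop is also left to the physician.

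Third, the analysis is descriptive and has no threshold, so no prespecified decision would change. That is correct, but the interval is still offered as the basis for generalising.

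Fourth, nothing says the sites are a random sample, so clustering by site would not by itself secure inference to the target population. That is also correct. A clustered interval removes one source of overstatement, not all of them.

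A reader might infer that the plan fails its own precision criterion. It does so only if the word width is taken as full width: 2 × 5.19 = 10.4 points is already 14.8% of 70%, so a DE above 1.025 would pass 15%. The plan does not apply the criterion that way.

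**Conclusion.** The concern holds as a conditional omission. The primary interval and the planned precision both set within-site correlation to zero, in a multi-centre study whose endpoint partly reflects physicians' decisions and whose interval is meant to reach beyond the participating sites. Any positive within-site correlation makes the interval too narrow. The size is unknown: under the assumed 15 to 60 equal sites and ICC 0.01 to 0.10, the half-width is about 5.3 to 8.8 points and coverage about 94.5% down to 75%.

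Two stronger readings are tempting. One is that ±5.2 is a miscalculation; it is not, since it is exact under independence. The other is that the stated precision is certainly lost to a degree that matters. The documents do not show that: the loss can be a tenth of a point, and the conclusion that precision is reasonable survives across the whole assumed range. This is a worthwhile and inexpensive improvement, not a defect that undermines the primary result.

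**What to change.** In SAP 2.5.2, 2.7.2 and 5.4.1, prespecify a 95% interval with site as the cluster for the month 6 and month 12 proportions, for example PROC SURVEYFREQ with a CLUSTER statement for site and a small-sample correction in case sites are few. Report it beside the simple binomial interval, and say that the clustered one is used when generalising to the target population. Prespecifying both avoids choosing between them after seeing the data.

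In Protocol 9.6 and SAP 3, state that ±5.2 points assumes no clustering, and give the range of half-widths under the planned number of sites and an assumed range of ICC.

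The cost is SAP wording, a few lines of code and an interval that may be wider, modestly or, with few sites and a high ICC, considerably. No extra patients or data are needed, because site can be read from the patient identifier: "Each patient is uniquely identified by a Subject Number which is composed by the site number".

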2.5.3 Handling of missing values/censoring/discontinuations

There will be no replacement or imputation of missing values. All analysis will be conducted on observed cases only. For patients lost to follow up after achieving the LCZ696 dose of 97 mg sacubitril / 103 mg valsartan bid, the conservative approach will be used, according to which they will be considered as not staying on treatment.

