#### 9.4 Analysis of the primary and key secondary variable(s)

#### 9.4.1 Variable(s)

#### 9.4.1.1 **Primary Outcome Analysis**

The primary outcome measure of the study will be the proportion of patients remaining on treatment with LCZ696 97 mg sacubitril / 103 mg valsartan at six months of follow up. The proportion will be calculated as the number of patients at 97 mg sacubitril / 103 mg valsartan over the total number of patients that received at least one dose of ENTRESTOTM.

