2.7 Analysis of secondary efficacy objective(s)

2.7.1 Secondary endpoints

The following secondary outcome measures will be analyzed:

- 1. The proportion of patients who tolerate the LCZ696 dose of 97 mg sacubitril / 103 mg valsartan mg bid at 12 months of treatment.
- 2. The proportion of patients on LCZ696 who had required down-titration after reaching the 97 mg sacubitril / 103 mg valsartan
- 3. The number of down-titration changes from 97 mg sacubitril / 103 mg valsartan during 12 months of treatment.
- 4. Functional capacity as measured by the change from baseline to 6 months and 12 months in the Six Minute Walk Test.
- 5. Time to each up-titration to 49 mg sacubitril / 51 mg valsartan and 97 mg sacubitril / 103 mg valsartan.
- 6. Duration of treatment on each dose of LCZ696.
- 7. The proportion of patients on guideline-recommended doses and who are tolerant of beta-blockers and MRAs at baseline, 6 and 12 months.

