2.7.3 Handling of missing values/censoring/discontinuations

There will be no replacement or imputation of missing values. All analysis will be conducted on observed cases only. For patients lost to follow up after achieving the LCZ696 dose of 97 mg sacubitril / 103 mg valsartan bid, the conservative approach will be used according to which they will be considered as not staying on treatment.

A sensitivity analysis could be conducted for the PPS as required.

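### The observed-case rule in SAP 2.5.3 is not reconciled with the all-dosed denominator of the primary proportion, and the per-protocol check cannot isolate the lost-to-follow-up assumption it is meant to test

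*SAP*

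**What the plan says.** **Denominator.** SAP 2.5.1 divides the number at 97/103 mg "over the total number of patients that received at least one dose of LCZ696". Protocol 6.4.1 gives the same calculation, and so does protocol 9.4.1.1: "over the total number of patients that received at least one dose of" the product. Protocol 9.1 and SAP 2.2 make the FAS (all dosed patients) the primary set. Protocol 9.6 works on the full number: "With 300 patients enrolled in the study, the 95% Confidence Interval width will be" ±5.2 points.

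**Missing data.** SAP 2.5.3 reads: "There will be no replacement or imputation of missing values. All analysis will be conducted on observed cases only". Its only exception is that patients lost to follow-up after reaching 97/103 mg bid are treated as having left treatment. Protocol 9.4.6 has the same rule and exception. SAP 2.7.3 repeats both for the secondary endpoints ("All analysis will be conducted on observed cases only"), which include "The proportion of patients who tolerate the LCZ696 dose of 97 mg sacubitril / 103 mg valsartan mg bid at 12 months".

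**Per-protocol check.** Protocol 9.4.6 plans, without condition, a PP-only analysis to test the effect of the lost-after-target assumption. SAP 2.5.4 plans a PPS analysis only if the two sets differ by more than 10%, and does not link it to that assumption. SAP 2.7.3 says: "A sensitivity analysis could be conducted for the PPS as required". Protocol 9.1 and SAP 2.2 each contain two statements: that the PP analysis is repeated when the sets differ by more than 10%, and that all analyses are run in both sets unless otherwise specified.

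**The concern.** The observed-case sentence stands under the primary objective and covers all analysis, so it cannot be read as applying only to other endpoints. It meets a denominator that includes everyone dosed, and nothing says which prevails. Two programmers following SAP 2.5.1 and 2.5.3 to the letter could report different primary figures.

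The literal rule also works in an odd direction. A patient who reached target and was then lost counts as a failure, while one lost before ever reaching target drops out. Removing patients who are not at target can only raise the proportion, and the study's question is how many patients tolerate the target dose.

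The sensitivity analysis does not repair this. It is meant to show how much the lost-after-target assumption matters, but it changes several groups of patients at once.

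**Working it through.** **1. The plan's own precision.** Inputs from protocol 9.6: 70% expected, 300 patients, 95% interval. Half-width = 1.96 × √(0.70 × 0.30 / 300) = 5.19 points, giving 64.8% to 75.2%. This reproduces the stated figure and uses all 300 in the denominator.

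**2. The two readings by type of patient at month 6.**

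| Patient | All-dosed (SAP 2.5.1) | Literal SAP 2.5.3 |
|---|---|---|
| Documented at target | success | success |
| Documented on a lower dose | failure | failure |
| Documented stop | failure | failure |
| Lost after reaching target | failure | failure, by the exception |
| Lost before reaching target | failure | out of the denominator |

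Stops are treated as observed because protocol 5.5.5, 5.5.6 and 5.5.10 require dose changes and reasons for withdrawal to be recorded.

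**3. Size of the difference.** Neither document gives a dropout rate, so k, the number lost before target, is an assumption. With 210 at target, the literal proportion is 210 / (300 − k):

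- k = 0: 210/300 = 70.0%
- k = 5: 210/295 = 71.2% (+1.2 points)
- k = 10: 210/290 = 72.4% (+2.4 points)
- k = 15: 210/285 = 73.7% (+3.7 points)

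**4. What the PP comparison measures.** The PPS is made up of patients who complete the month-6 assessments (SAP 2.2). Under protocol 5.5.6, a patient who stops drug completely should also leave the trial, so such patients generally fall out. SAP 5.5 removes major deviators as well. Assumed counts, ignoring deviations and taking none of the stopped group as month-6 completers: 195 at target, 45 on a lower dose, 15 lost after target, 10 lost before target, 35 stopped or left for other reasons; total 300.

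- Plan's assumption, all dosed: 195/300 = 65.0%
- Only the 15 counted as on target: 210/300 = 70.0% (+5.0 points)
- Only the 15 excluded: 195/285 = 68.4% (+3.4 points)
- PPS: 195/(195 + 45) = 195/240 = 81.25% (+16.25 points)

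Now suppose nobody was lost after target and the 15 do not exist. The FAS gives 195/285 = 68.4% and the PPS still gives 81.25%, a gap of 12.8 points that owes nothing to the assumption under test.

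**5. The 10% trigger.** The text does not say what is compared. With 210/300 at target and every removed patient off target, the first number removed that exceeds 10% is:

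- relative change in the result: 28 (210/272 = 77.2%, above 77.0%)
- size of the set: 31 (31/300 = 10.3%)
- absolute points: 38 (210/262 = 80.2%, above 80.0%)

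**The case against.** The best answer is that a specific formula governs a general sentence. The denominator is written three times, the FAS is the primary set, and precision is computed on 300. On that view the lost-to-follow-up sentence only settles the numerator for patients whose last recorded dose was 97/103 mg. Those lost before target were never candidates for the numerator and need no rule. This is coherent and probably what was meant. It does not remove the problem, because SAP 2.5.3 applies its rule to all analysis and no text subordinates it.

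Five stronger readings are tempting, and the documents do not support them.

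- **The primary denominator is missing or wrong.** It is stated and suitable; what is lacking is a precedence rule.
- **Every patient without a month-6 visit would be dropped** (at an assumed 10%, 210/270 = 77.8%). Stops are recorded, patients lost after target stay in as failures, and protocol section 6 seeks treatment status and dose by telephone.
- **The sample code in SAP 5.4.1 decides the matter.** The line "tables <xxx> / binomial" is optional code with a placeholder variable and fixes no denominator.
- **Month 12 is a second contradiction.** SAP 2.7.1 gives no denominator there, but protocol 9.4.4 introduces that proportion as handled in the same way as the primary. It needs only a clarifying phrase.
- **The SAP introduced the trigger, or the PP result might never be shown.** The trigger is already in protocol 9.1, and both documents also say that all analyses are run in both sets. The fault is that these statements conflict.

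It is also fair that the set-size and relative-result readings of the trigger nearly coincide (31 against 28), and that the study is descriptive with no hypothesis test.

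**Conclusion.** The concern holds as a failure to reconcile two rules. Followed literally, SAP 2.5.3 and protocol 9.4.6 take patients lost before target out of the primary denominator and push the estimate up. For 5 to 15 such patients the rise is 1.2 to 3.7 points from 70.0%. At 10 patients it is 2.4 points, under half the planned half-width of 5.2. These figures assume that 210 of 300 are at target and that all documented stops are kept as failures; the number lost is assumed.

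The second part does not depend on the counts. A completer set with deviators removed changes more than the lost-after-target patients, so it cannot show what that assumption alone contributes. The condition for running the PP analysis is inconsistent within protocol 9.1 and within SAP 2.2, and across protocol 9.4.6 and SAP 2.5.4 and 2.7.3. This should be corrected, because the primary result is one proportion and its denominator should have one reading.

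**What to change.** - In SAP 2.5.3 and 2.7.3 and protocol 9.4.6, state that for the dose-proportion endpoints at months 6 and 12 all FAS patients stay in the denominator, and that anyone not documented on 97/103 mg bid at that time point counts as not on target. Limit the observed-case rule to the six-minute walk, laboratory and vital-sign summaries.
- Test the lost-to-follow-up assumption within the FAS. Change only the status of patients lost after reaching target, for example counted as on target or excluded, and keep documented stops and deaths as failures.
- Report the PPS as a supportive completer analysis. Give one rule for when it is run, worded identically in protocol 9.1 and 9.4.6 and SAP 2.2, 2.5.4 and 2.7.3. If a 10% trigger is kept, say what is compared.

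The cost is SAP wording, a protocol clarification and one small extra table, with no new data. The reported proportion may be less favourable than under the observed-case reading.
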